University of Florida IRB-02 Protocol Template Guidelines

The “protocol” is similar in form to a brief research proposal. It should be as concise as possible. It should, however, contain all information relevant to the proposed research project not specifically covered in the SmartForms. (Not every item will be relevant for every project, of course, and you may limit responses as appropriate in such cases, but if you’re uncertain as to what to include, be “inclusive” as that makes it less likely we’ll have requests for additional information.)

1. Background:

- **Colorectal cancer (CRC)** accounts for about 8% of new cancer cases in the US.¹ Alcohol and red/processed meat consumption are two diet-related risk factors for CRC.²⁻⁴ Evaluating nutritional status is considered a key component of the patient care process⁵ and when done effectively can help patients understand what foods increase CRC risk. Informing patients of personal nutrition risk factors for CRC may also help to stimulate accurate CRC risk perceptions and facilitate CRC prevention behaviors including screening. For some populations, including rural adults, technology can help address factors that contribute to CRC disparities such as low screening rates, poor diet, low literacy, and limited access to healthcare.
- Innovative technology can facilitate communication of dietary risk factors in a medical setting, which is often difficult due to measurement challenges and barriers related to patient and provider characteristics. Physicians own interest in nutrition, hours of nutrition education received, and personal fruit and vegetable intake impact frequency of nutrition counseling with patients.^{7,8} **Virtual health assistants (VHAs)** are human-like avatars that talk to and collect information from users in a web-based setting. There is growing evidence that using VHAs can facilitate discussions of stigmatized health information,⁹ offer advantages over traditional patient-provider settings,¹⁰ and integrate into existing healthcare systems.¹¹ Furthermore, racial minorities and rural adults can benefit from innovative nutrition interventions for CRC prevention as they experience poorer adherence to dietary guidelines,¹² higher incidence, morbidity, and mortality from CRC, and lower rates of screening compared to others.^{13,14} Thus, a strategic nutrition communication intervention using VHT is a promising approach for enhancing nutrition communication for CRC prevention.
- This proposal is a subproject of a currently approved study (PI, [name]), titled “A Patient-centered Intervention Using Technology to Reduce Colorectal Cancer Disparities in Primary Care” (1R01CA207689-01A1) (IRB#201702765 and IRB#201601642). The goal of the parent project is to test the efficacy of a patient-centered, tailored message intervention for increasing CRC screening among racial minorities and rural patients. Given the challenges of discussing nutritional risk in a clinical setting, the objective of this proposed subproject is to test if tailored nutrition-risk information delivered in a web-based platform increases perceptions of CRC risk and CRC prevention behaviors.

2. Specific Aims:

- The goal of this proposed project is to adapt an existing CRC screening intervention to include a nutrition module that engages users with information about alcohol and red/processed meat consumption, and delivers tailored nutrition-risk messages to enhance CRC prevention outcomes.
- The objective of this proposed project is to pilot test the adapted VHT-delivered, tailored, nutrition-risk module to investigate mechanisms of efficacy for the adapted intervention including establishing preliminary estimates for CRC risk perceptions and CRC prevention behaviors. This information will be used to inform a larger trial.
- The hypothesis is reporting dietary intake and receiving personalized nutrition-risk factors for CRC via a VHA will increase perceptions of CRC risk, CRC screening intentions, and information seeking behaviors (e.g. reducing alcohol, red/processed meat, how to order at home screening kit).
- **Aim 1:** Modify an existing CRC intervention with a nutrition module where VHAs collect dietary intake information and give tailored visual feedback on nutrition risk factors for CRC. To increase patient engagement with nutrition-risk messages delivered in a virtual setting, we must first understand beliefs, experiences, and evaluations of nutrition-risk communication. We will engage in a cultural adaptation of an interactive nutrition module delivered by virtual health assistants (VHAs) to ensure acceptable social reactions to reporting dietary intake of alcohol and red/processed meat and receiving personalized feedback in the virtual setting. We will also conduct content adaptation of the module (tailoring language, visuals, and examples of food items).
- **Aim 2:** Pilot test the VHA intervention to assess if the tailored nutrition module increases (2a) accurate risk perceptions for CRC (2b) intentions to screen for CRC (2c) and information seeking behaviors (e.g. how to reduce alcohol and red/processed meat intake, how to order home screening kit).

3. Research Plan / Study Description:

Aim 1

Eligibility Criteria:

- Eligible adults will be between 50-73 years old, proficient in English and geographically rural areas of north central Florida. We will enroll black, white, male and female participants.

Focus Group Structure:

- Adults at risk for CRC will participate in focus groups with an estimated 6 groups comprised of approximately 6 people. (N=36)
- Focus groups will be conducted via an iterative cycle of adaptation based on participant feedback:
 - Cycle 1: FG 1 and 2 use storyboard exercise and discussion to inform initial content and message preferences for nutrition module → PI meet with graphic designer/VH team to develop initial prototype
 - Cycle 2: FG 3 and 4 comment on developed first round stimuli from graphic designer/first prototype of module → PI meet with graphic designer/VH team to modify module
 - Cycle 3: FG 5 and 6 comment on module version 2 → PI meet with graphic designer/VH team to update
- Focus groups will take place in the community at an accessible location, take approximately two hours, and will be video and audio-recorded.
- Due to Covid-19, as of Fall 2020 we will be conducting focus groups via zoom.
- Trained researchers will conduct the focus groups using a semi-structured guide based on the Cultural Sensitivity Model (Resnicow, 2000).
- Participants will answer questions to inform acceptability of messages and graphics to be delivered in the virtual setting related to CRC risk. Participant responses will help adapt the VHT nutrition module for cultural appropriateness, content, and framing of nutrition communication.
- A questionnaire assessing participant characteristics, perceptions, and behaviors will also be administered.

Individual Think-aloud Interview Structure:

- A usability test of the nutrition module will be achieved by conducting individual, in audio and video-recorded think-aloud interviews (N=12) rooted in user-centered design principles.
- Due to Covid-19, as of Fall 2020 we will be conducting interviews via zoom.
- Think-aloud interviews will continue using the iterative process:
 - Cycle 4: TA 1-4 conducted on module version 3 → PI review data, make decision about content/functionality, etc., and continue agile design method as needed through TA 5-8 and TA 9-12
- Interviews will take place remotely, via zoom, take approximately one hour, and will be video and audio-recorded.
- Facilitated by trained researchers, participants will test the VHA delivered intervention on a web-enabled device and will be encouraged to verbalize thoughts, questions, opinions and concerns about the module.

- Results from think-aloud interviews will inform final adaptations needed for the nutrition module prior to pilot-testing.
- A questionnaire assessing participant characteristics, perceptions, and behaviors will be administered.

Data and analysis

- Focus group and interview data will be transcribed verbatim using secured transcription service DataGain, Inc. (reviewed by UF Integrated Risk Management and classified as low risk) and managed with qualitative data management software. The PI and trained members of the research team will analyze qualitative data using a constant comparative method and iterative process throughout data collection phase.
- Transcripts will be analyzed for a priori and emergent themes relevant to nutrition module adaptations needed including but not limited to a) surface culture adaptations, b) deep culture adaptations c) cognitive adaptations d) affective-motivational adaptations.
- Questionnaire data will be analyzed to summarize participant characteristics, perceptions, and behaviors. We will conduct descriptive statistics (e.g. Means, SDs) using quantitative data analysis software.
- A member of the research team will store electronic data files (i.e. transcripts, audio and video files, data spreadsheets) on a password protected and encrypted server.

Aim 2

Eligibility Criteria:

- Eligible rural (based on zip code) adults will be between age 45-73 years old, residents, who have not had CRC and who have not obtained CRC screening based on guidelines (i.e. <10 years for colonoscopy, <1 year for stool test, < 5 years for sigmoidoscopy). Participants should also answer “yes” to the question, do you have health insurance? We will enroll equal proportions of black, white, male and female participants.

Pilot Test Structure:

- We will enroll participants using Qualtrics Panels. Qualtrics Panels consist of U.S. adults who have agreed to participate in web administered surveys.
- We will pilot-test the module using a 3-group randomized design with 30 participants per group. Participants will be randomized to one of three groups: 1) high interactive VHA administered nutrition module, 2) low interactive VHA module, or 3) attention control module. Each module will be approximately 5-10 minutes.
- For group 1, the VHA will interactively collect nutrition information (alcohol, red meat, and processed meat intake) and report risk information back to users in visual and audio format. Group 2, will complete the current intervention module that includes items assessing alcohol and meat intake.

This module is consistent with [name] ongoing clinical trial work. Groups 1 and 2 will receive CRC prevention messages including information about how to use a home FIT screening test (delivered by the VHA).

- Group 3, the attention control group, will complete a non-CRC related module (e.g. recycling).
- All groups will complete a questionnaire assessing outcomes of interest and participant characteristics.
- All participants will access the intervention using an electronic link sent to them via email.
- Participants will have option to receive additional information (see outcome 3 below). Those participants will be directed to evidence-based cancer prevention resources housed on the secure web platform Wix.com.

Data and analysis:

- We will assess three main outcomes variables:
- (1) Accurate risk perceptions for CRC (e.g. items measured on a 7-point Likert scale, "My chance of getting CRC are high", "FIT screening decreases my chances of dying from cancer").³⁰
- (2) Intentions to screen for CRC (e.g. items measured on a 7-point Likert scale "I want to get screened for colon cancer" or "I will talk to my doctor about colon cancer screening with FIT").³¹
- (3) Information-seeking behavior (e.g. assessed via clicks on links regarding "reducing alcohol/meat consumption", "how to order a FIT kit" (for intervention groups) or "tips for recycling" (for attention control group). We will use the Qualtrics "event tracking" feature to track clicks (yes/no).
- For outcomes (1) and (2) we will conduct one-way ANOVAS or Kruskal-Wallis test on the difference between baseline and post-test to obtain estimates to inform the larger trial.
- For outcome (3) we will use Pearson's chi-square test or Fisher exact test.
- Sample size was determined using a stepped rule of thumb based on an expected small effect size and 90% power for the future trial (Bell, Whitehead, & Julious, 2018). Based on this approach, if we expect a small effect size (.1-.3) at 90% power (for the larger trial) the pilot would require n=25 per arm to obtain estimates to inform larger trials sample size. Thus, n=30 per arm (N =90) is expected to give appropriate estimates to inform the larger trial.
- Data will be de-identified, stored with participant IDs on UF secure server accessible from PI's password protected computer, and analyzed using quantitative data analysis software for, preliminary estimates to plan a larger trial (e.g. confidence interval estimates, recruitment/response rates) and descriptive statistics to describe participant characteristics.
- Descriptive statistics will be calculated for all variables including mean, standard deviation, median, inter-quartile range, minimum and maximum for

continuous variables and frequency and proportion for categorical variables. Graphical illustration will be provided if applicable.

- Data analytics obtained from wix.com will be reviewed to understand use. Descriptive statistics on resources clicked and time spent on the site will be calculated.

4. Possible Discomforts and Risks:

- There are no potential risks of physical, psychological or economic harm associated with participant in this study.

5. Possible Benefits:

- While no direct benefits are expected, participants may benefit from learning about their health and ways to engage in health prevention behaviors relevant to nutrition and cancer screening.
- The risks to subjects are reasonable in relation to the anticipated benefits due to the importance of the knowledge that will be gained from this research to benefit future populations.

6. Conflict of Interest:

- There are no real or potential conflicts of interest with any investigators with regard to this specific research project.

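### Aim 2 sets enrolment by race and sex but describes no use of either factor in allocation or analysis; stratifying and adjusting would be a small improvement needing no extra participants

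*Combined protocol and SAP*

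**What the plan says.** All references are to section 3 of the combined protocol and SAP, under Aim 2.

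- **Eligibility Criteria:** "We will enroll equal proportions of black, white, male and female participants".
- **Pilot Test Structure, recruitment:** "We will enroll participants using Qualtrics Panels".
- **Pilot Test Structure, design:** "We will pilot-test the module using a 3-group randomized design with 30 participants per group", followed by "Participants will be randomized to one of three groups". No sequence generation, blocking or stratification is described.
- **Data and analysis:** outcomes 1 and 2 (risk perceptions and screening intentions) are compared across arms by one-way ANOVA or Kruskal-Wallis on the change from baseline to post-test. Outcome 3 (clicks on information links) is compared by a chi-square or Fisher test. None of these has a race or sex term.
- **Sample size:** "n=30 per arm (N =90) is expected to give appropriate estimates to inform the larger trial".

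**The concern.** To meet its own enrolment target, the study must know each participant's race and sex at entry. It fixes the balance of these factors for the sample as a whole, where no comparison is made. Between arms, where the comparison is made, neither the described allocation nor the analysis secures it.

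In arms of 30, sizeable chance differences in race or sex mix are common. If either factor is related to how much a participant's answers change, an unadjusted contrast carries noise that could be removed using data already collected. The pilot exists to supply estimates for a larger trial, so avoidable noise is worth removing when it costs almost nothing.

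**Working it through.** **Inputs from the protocol.** Three arms of 30, and equal enrolment by race and by sex. The plan's total reproduces: 3 × 30 = 90. Equal proportions then give 45 Black and 45 White participants, and 45 men and 45 women.

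**Assumptions.** Arm sizes are held at exactly 30, as the protocol states. Allocation within that limit ignores race and sex; the protocol does not say whether it does.

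**1. How often the arms would differ.** Let a, b and c be the numbers of Black participants in the three arms, with a + b + c = 45. Under unstratified allocation

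P(a, b, c) = C(30,a) · C(30,b) · C(30,c) / C(90,45).

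Summing over the relevant combinations:

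| Event | Race alone | Race or sex |
|---|---|---|
| Largest minus smallest arm at least 6 of 30 (20 percentage points) | 0.325 | 1 − (1 − 0.325)² = 0.545 |
| Groups 1 and 2 differ by at least 5 of 30 | 0.248 | 1 − (1 − 0.248)² = 0.434 |

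The last column treats the two factors as independent. A simulation with race-by-sex cells of 23/22/22/23 gave 0.546 for the first row.

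**2. What such a gap does to one estimate.** The documents give no figure for how far race or sex shifts the change score, so take d = 0.2 to 0.5 SD as an assumed range. A 20-point gap moves a pairwise contrast by 0.20 × d:

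- d = 0.2: 0.04 SD
- d = 0.3: 0.06 SD
- d = 0.5: 0.10 SD

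The standard error of that contrast is √(2/30) = 0.26 SD.

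**3. Average gain in precision.** A two-level factor split 50:50 contributes d²/4 to the variance of the change score (total variance 1). Balancing and adjusting for it removes about that share:

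- d = 0.2: 0.04/4 = 1.0%
- d = 0.3: 0.09/4 = 2.25%
- d = 0.5: 0.25/4 = 6.25%

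That is about 1-6% of variance per factor. In standard-error terms, 1 − √(1 − d²/4) runs from 0.5% to 3.2%.

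**4. Whether stratification works at N=90.** Four equal cells would need 90/4 = 22.5 each, so exact equality is impossible. There are two workable versions.

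- *Cells of 24 Black men, 21 Black women, 21 White men and 24 White women.* These sum to 90 and keep 45/45 on each factor (24 + 21). Each is a multiple of 3, so every arm receives 8 + 7 + 7 + 8 = 30, with 8 + 7 = 15 Black participants and 15 men.
- *Cells of 23/22/22/23 in blocks of 3.* Each cell gives every arm 7, with 2 + 1 + 1 + 2 = 6 participants left over. An arm can take at most one from each cell, so arms range from 28 to 32. In simulation the largest race gap between arms was about 7 percentage points.

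**The case against.** **Silence is not a stated choice.** The protocol does not say that allocation is simple or that race and sex are ignored. It is a concise ethics-board template that leaves some material to forms we do not have. This stands: the finding is that no use of the factors is described, not that they are known to be unused.

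**Arm sizes.** A reader might infer that arm sizes are left to chance and could fall short of the figure in "the pilot would require n=25 per arm". The documents do not support this. The design sentence sets 30 per group and the sample-size paragraph repeats it. Only the mechanism is missing.

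**Bias.** A reader might also infer that the comparison is confounded. It is not. Chance imbalance under valid randomisation causes no bias in expectation, and the usual standard error already allows for it. Analysing change from baseline also removes stable race or sex differences in outcome level; only differences in change matter.

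**Small effect.** It is tempting to set the imbalance against the expected effect of 0.1-0.3, but the protocol ties that range to the larger trial ("if we expect a small effect size (.1-.3) at 90% power (for the larger trial"). The pilot is for estimation, and stratifying does not alter what it can detect. The average gain is a few per cent of variance at most per factor, and the protocol does not name race or sex as prognostic for change. This stands, and it is why the point is minor.

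**Limits of the remedy.** If equal proportions means four equal race-by-sex cells rather than equal margins, targets of 24/21/21/24 depart from it. Dropout after randomisation can disturb exact balance. Covariate terms have no place in the Kruskal-Wallis alternative. All three stand as limits; none makes the stratified design materially worse than plain randomisation with an unadjusted test.

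**Conclusion.** The point holds as a minor design improvement. The plan enrols by race and sex, describes no use of either in allocation, and does not adjust for them. With 30 per arm enforced and allocation unstratified, a gap of 6 or more of 30 between some two arms would arise on race in about 33% of trials, and on race or sex in about 55%.

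The frequency is high but the consequence is modest: no bias, and a gain of about 1-6% of variance per factor. That range rests wholly on the assumed shift of 0.2-0.5 SD. The 33% assumes a 45/45 split and arms of exactly 30; the 55% also treats the factors as independent. If allocation is in fact already stratified, the only changes needed are to say so and to add the model terms.

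**What to change.** 1. In Pilot Test Structure, state how the allocation sequence is generated and how 30 per group is reached.
2. Randomise within the four race-by-sex strata in permuted blocks of 3. If the survey tool does the allocation, an even-allocation randomiser within each stratum serves the same purpose. Keep N=90.
3. Say whether equal proportions means margins or crossed cells. If margins, cell targets that are multiples of 3, such as 24/21/21/24, give exact balance. Otherwise accept near-exact balance, with arms of 28-32. Both are subject to dropout.
4. For outcomes 1 and 2, replace the one-way ANOVA with a linear model of the change score on arm, race and sex. Without these terms, the standard error after stratified allocation is slightly too large. Kruskal-Wallis, if used, remains unadjusted.

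**Cost:** survey set-up, a few lines of protocol text, and two residual degrees of freedom (90 − 3 = 87 becomes 90 − 5 = 85). No extra participants are needed.

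### Only Group 1 versus Group 2 bears on the nutrition module, yet the hypothesis, the planned tests and the estimate for the larger trial are not tied to that contrast

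*Combined protocol and SAP*

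**What the plan says.** Section 2 (Specific Aims) gives a joint exposure: "The hypothesis is reporting dietary intake and receiving personalized nutrition-risk factors for CRC via a VHA will increase perceptions of CRC risk", together with screening intentions and information seeking. The same section sets the pilot objective as "to investigate mechanisms of efficacy for the adapted intervention including establishing preliminary estimates for CRC risk perceptions and CRC prevention behaviors", to inform a larger trial. Aim 2 puts the question differently: "Pilot test the VHA intervention to assess if the tailored nutrition module increases (2a) accurate risk perceptions for CRC", and likewise for the other two outcomes.

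Section 3, Aim 2, Pilot Test Structure sets up a "3-group randomized design with 30 participants per group", with arms "1) high interactive VHA administered nutrition module, 2) low interactive VHA module, or 3) attention control module". Their content is:

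- Group 1 receives the new module: "the VHA will interactively collect nutrition information (alcohol, red meat, and processed meat intake) and report risk information back to users". The feedback is both seen and heard.
- Group 2: "Group 2, will complete the current intervention module that includes items assessing alcohol and meat intake".
- Groups 1 and 2: CRC prevention messages from the virtual assistant, including how to use a home FIT test.
- Group 3: a module unrelated to CRC.

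Under Data and analysis, outcomes 1 and 2 are compared by one-way ANOVA or Kruskal-Wallis on the change from baseline, and outcome 3 by chi-square or Fisher exact test. No pairwise contrast is named as the answer to Aim 2 or as the estimate to take forward.

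**The concern.** The hypothesis and Aim 2 each name a cause, and the arms do not separate that cause from other content.

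Reporting intake comes first in the hypothesis, but both assistant-delivered arms ask about intake, so a comparison of Group 1 with Group 2 says little about it. The comparisons that do include reporting are those with Group 3, and they also include the CRC and FIT messages. Those messages bear directly on what is measured: the example items concern whether FIT lowers the chance of dying from cancer and whether the person will discuss FIT with a doctor, and one tracked link concerns ordering a kit. A general effect of the messages could show up in all three outcomes and look like an effect of the nutrition module.

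At stake is what the pilot may conclude and which effect estimate goes into planning the larger trial. A positive three-group result would not by itself support either the hypothesis or the Aim 2 statement.

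**Working it through.** **Inputs from the documents.** Three arms of 30 give 3 × 30 = 90, which matches the stated total. The expected effect for the larger trial is 0.1 to 0.3. The significance level is not stated; 5% (two-sided for pairwise comparisons) is assumed here. The cited rule behind 25 per arm is not reproduced in the protocol and is not needed for this point.

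**What each contrast contains.** Let r = being asked about intake, f = personalised risk feedback, i = interactive collection by the assistant, and m = the CRC and FIT messages. Assume additive effects, and for the moment that Group 2 receives no personalised feedback.

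| Contrast | Components |
|---|---|
| Group 1 − Group 2 | f + i |
| Group 1 − Group 3 | r + f + i + m |
| Group 2 − Group 3 | r + m |

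In Group 1 − Group 2, r and m cancel. In every contrast that contains r, m is present too. If Group 2's module does return some feedback f₂, the first row becomes (f − f₂) + i, and part or all of the feedback effect also cancels. Under either assumption, Group 1 − Group 2 is what the adapted module adds to the current one, and contrasts with Group 3 are effects of a whole package.

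**What the three-group ANOVA responds to.** With 30 per arm and SD 1, the noncentrality is λ = 30 × Σ(μ − μ̄)².

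- Messages alone, means (m, m, 0): λ = 30 × (2/3)m² = 20m².
- Module alone, means (x, 0, 0): λ = 30 × (2/3)x² = 20x².

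The two expressions are the same, so the test is as sensitive to a shared message effect as to a module effect of equal size and cannot tell them apart. Rejection probabilities with 2 and 87 degrees of freedom at 5%, for assumed effects:

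| Message effect (SD) | Module effect (SD) | λ | P(reject) |
|---|---|---|---|
| 0 | 0.3 | 20 × 0.09 = 1.8 | 0.20 |
| 0.2 | 0 | 20 × 0.04 = 0.8 | 0.11 |
| 0.5 | 0 | 20 × 0.25 = 5.0 | 0.49 |

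In the last two rows Group 1 − Group 2 is zero.

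**Precision of Group 1 − Group 2.** The 95% half-width is 1.960 × √(2/30) = 0.506 SD of the change score, which is wider than the whole expected range of 0.1 to 0.3.

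**The case against.** The strongest reply is that Aim 2 and the project goal are package questions. The study adapts an existing intervention by adding a nutrition module, and both adapted-versus-current and package-versus-attention-control are legitimate comparisons. That stands: the design is informative, and all three arms are worth keeping. It does not settle which comparison answers Aim 2, and the planned three-group tests do not choose one.

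Second, the hypothesis specifies that the exposure comes through the assistant. If reporting means reporting interactively to the assistant, then i belongs to the exposure and Group 1 versus Group 2 comes close to testing it. This is a fair reading. It supports tying the hypothesis to that contrast rather than leaving it unattached. The component table depends on how the ingredients are defined and on additivity.

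Third, the protocol is silent on feedback in Group 2; it does not say there is none. The parent project is described as using tailored messages, so the current module may return some. The f + i line is therefore conditional.

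A reader might also infer that the arm names present interactivity as the only difference. They do not: only Group 1's label mentions a nutrition module, and the text goes on to describe each arm's content.

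Finally, a reader might infer that the larger trial will be wrongly sized by a known amount. With n per arm = 2 × (1.960 + 1.2816)²/d² = 21.015/d², an effect of 0.30 needs 234 per arm. Adding an assumed message effect of 0.20 gives 0.50, which needs only 85. But the component sizes are invented, and nowhere does the protocol say that the Group 1 versus Group 3 difference will be used as the module effect. The arithmetic illustrates a risk and is not a forecast.

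**Conclusion.** The point holds as a mismatch between the claim and the contrasts. Intake items appear in both assistant-delivered arms, and the CRC and FIT messages are common to both. A three-group result, or Group 1 versus Group 3, therefore cannot be credited to the nutrition module, and Group 1 versus Group 2 shows only its addition to the current module. Naming that contrast without rewording the hypothesis would leave reporting of intake as a claimed cause that the contrast does not test.

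No figure in the plan is wrong. The size is illustrative: about 49% rejection with no module effect if the messages are worth 0.5 SD, and about 11% at 0.2 SD, assuming 5% significance, equal SDs and 30 analysed per arm.

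A reader might take the objective of investigating mechanisms as a promise to separate the ingredients, and so conclude that the pilot fails. The text states an objective that includes preliminary estimates; it does not promise separation. This is an inexpensive improvement that changes what the pilot can conclude, not a fatal flaw.

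**What to change.** Keep the three arms and make four changes to the text.

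1. Restate the Aim 2 hypothesis along these lines: *compared with the current module, which already asks about alcohol and meat intake, the adapted interactive nutrition module with risk feedback increases the outcomes.*
2. Under Data and analysis, name Group 1 minus Group 2, with its 95% confidence interval, as the nutrition-module estimate carried to the larger trial.
3. State that contrasts with Group 3 are whole-package effects, including the CRC and FIT messages, and will not be used as the nutrition-module effect size.
4. In Pilot Test Structure, state whether Group 2's module returns personalised risk feedback, because the meaning of Group 1 versus Group 2 depends on it.

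This needs no new arm, participants or data. The downside is a narrower claim: the pilot would not test reporting of intake or interactivity as separate causes. The named estimate would also be imprecise at 30 per arm, and the interval should be reported so that this is visible.

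### As worded, outcome 3 counts clicks on colorectal cancer (CRC) links in Groups 1 and 2 but on a recycling link in the control group, so no contrast with Group 3 estimates an effect on CRC information seeking

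*Combined protocol and SAP*

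**What the plan says.** In Section 2, Aim 2c names the behaviour of interest as "information seeking behaviors (e.g. how to reduce alcohol and red/processed meat intake, how to order home screening kit". The hypothesis in the same section says much the same: "information seeking behaviors (e.g. reducing alcohol, red/processed meat, how to order at home screening kit". Both concern cancer prevention topics only.

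Section 3, Aim 2, Data and analysis defines outcome 3 as a yes/no click on links about cutting down on alcohol or meat, and then splits the links by arm: "how to order a FIT kit' (for intervention groups) or 'tips for recycling' (for attention control group". The analysis is a "chi-square test or Fisher exact test"; the arms to be compared are not named.

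Under Pilot Test Structure, participants may ask for additional information, with a pointer to outcome 3. The plan then says: "Those participants will be directed to evidence-based cancer prevention resources housed on the secure web platform Wix.com". No arm is excepted.

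The data are to supply "preliminary estimates to plan a larger trial (e.g. confidence interval estimates, recruitment/response rates".

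**The concern.** A randomised comparison estimates an effect on an outcome only if every arm has that outcome measured in the same way. Here the event counted as a yes changes with the arm. A control participant scores by clicking on recycling, which is not the Aim 2c behaviour, and nothing in the plan says that control is offered or scored on the CRC links.

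The pilot exists to inform a larger trial. A Group 3 click rate that reflects interest in recycling would give a difference from control that could be too large, too small or of the wrong sign, and that difference could be carried into the planning of the larger trial. If control is never shown the CRC links, the missing rate cannot be recovered after data collection. Reporting clicks link by link would show what was clicked but would not supply it.

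**Working it through.** **Inputs from the plan.** Three arms of 30; 3 × 30 = 90, which matches the stated total. Outcome 3 is binary. The plan gives no click rate, effect size or alpha for this outcome.

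**The texts side by side.**
- Target behaviour (Aim 2c, hypothesis): CRC prevention information.
- Counted in Groups 1 and 2: clicks on alcohol/meat or FIT-kit links. This matches the target.
- Counted in Group 3: clicks on a recycling link. This does not.
- Wix.com sentence: those who want more information go to cancer resources, whatever their arm. A control participant who clicks a recycling link does not fit it.

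The mismatch is therefore in the definition and does not depend on any assumed rate. The figures below only show how large it could be.

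**Method.** Assumptions: alpha 0.05, and a Pearson chi-square test across all three groups (2 df). The three-group test is inferred from the design. Rejection probabilities come from exact enumeration of three independent Binomial(30, p) counts, with X² = Σ(x − e)²[1/e + 1/(30 − e)] and e = total clicks/3.

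**1. No module effect, unequal number of links.** Assume two CRC links and one recycling link, each clicked with probability q, with within-person correlation ρ. P(any CRC click) = 2q − [q² + ρq(1 − q)]; P(recycling click) = q. For q = 0.2 and ρ = 0: 0.4 − 0.04 = 0.36 against 0.20, a spurious 16 points.

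| ρ | Any CRC click at q = 10/20/30% | Spurious difference (points) | Rejection |
|---|---|---|---|
| 0 | 19 / 36 / 51% | 9 / 16 / 21 | 14 / 27 / 38% |
| 0.5 | 14.5 / 28 / 40.5% | 4.5 / 8 / 10.5 | 7 / 10 / 13% |
| 1 | 10 / 20 / 30% | 0 | 4–5% |

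**2. No module effect, topics of different appeal.** The any-click rate is 30% in both CRC arms. If recycling is clicked by 20%, 40% or 50%, the apparent difference is +10, −10 or −20 points, and rejection is 13%, 13% or 37%.

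**3. A real effect, mis-scored.**
- True CRC rates 40%, 40% and 15%: power is 61% on common links. If control is scored on recycling clicks at 40%, it is 5%.
- True rates 40%, 25% and 10%: Group 1 minus Group 3 is 30 points. With recycling clicked by 5% to 50%, the recorded difference runs from +35 to −10 points.

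**4. Hypothetical effect on planning.** Suppose the larger trial were sized on this contrast at 90% power and two-sided 0.05, with n = (1.960 + 1.282)²[p₁(1 − p₁) + p₂(1 − p₂)]/(p₁ − p₂)² per arm.
- True 40% vs 15%: 10.51 × (0.24 + 0.1275)/0.0625, giving 62.
- Control recorded at 25%: 10.51 × (0.24 + 0.1875)/0.0225, giving 200.
- Control recorded at 30%: 10.51 × (0.24 + 0.21)/0.01, giving 473.

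**5. Group 1 versus Group 2.** Both arms have the same listed links. Under equal rates the 1-df chi-square test rejects about 5% of the time (0.048 to 0.054).

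**The case against.** The strongest reply is that the text is less definite than the concern. The links are given as examples, and the restriction to intervention groups could attach to the FIT link alone. The Wix.com sentence points to outcome 3 and may be loose wording meant for Groups 1 and 2. If instead it covers everyone, control might reach cancer resources after all. This stands as a reason to ask for clarification. It does not remove the problem: on the narrower parse, control still lacks the FIT link and can score on recycling.

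The plan names no contrast for outcome 3, and high versus low interactivity bears directly on Aim 2. That contrast is sound, but nothing says it is the one intended. A topic-matched link could also be a measure of general engagement; the plan does not say so, and that is not the Aim 2c behaviour.

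The plan will also review Wix.com analytics on resources clicked and time on site. It does not say these can be tied to participant or arm, and they cannot give a CRC rate for people who were not offered those resources.

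Finally, every rate above is assumed. Scenario 1 disappears under full overlap, the 5% power in scenario 3 follows from setting the recycling rate equal to the CRC rate, and the plan does not say the larger trial will be sized on clicks. Rejection rates also matter less in a pilot aimed at estimation. These points limit the weight of the numbers, but the outcome definition still differs by arm.

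**Conclusion.** The concern holds. On the outcome 3 wording, contrasts with Group 3, and any three-group test that includes it, do not estimate an effect on CRC information seeking. The direction and size of the error depend on interest in recycling and on how many links each arm sees, neither of which the plan fixes. Over the assumed rates, false rejection with no module effect ranges from about 5% to 38%.

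This should be fixed before data collection. It affects one of three main outcomes and leaves one valid contrast on it. The Wix.com sentence is a secondary point: the plan must say which links control sees and which clicks count for control.

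**What to change.** Once the post-test items for outcomes 1 and 2 are recorded, offer the same CRC links (reducing alcohol/meat, ordering a FIT kit) to all three groups. Define outcome 3 in every arm as a click on any CRC link, yes or no, and report clicks on any recycling link separately. State which arms the test compares, and make the Wix.com sentence agree with the link list.

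The cost is a small survey edit and two or three sentences in the plan. The order matters: the plan does not say where the links appear, and if control saw CRC links before the post-test, outcomes 1 and 2 could be affected.

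If control is not to be shown CRC links, restrict the outcome 3 comparison to Group 1 versus Group 2 and describe control clicks only. That gives no control estimate, and power is low: about 39% for assumed rates of 40% versus 20% with 30 per arm.
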